Sweet consumption and subsequent sweet food preferences and intakes:

Analysis Plan

Study ID number: NCT05672017

Document date: 26.04.24.

Analysis Plan

Data

Participants are randomized to increase their sweet food consumption, decrease their sweet food consumption or make no change to their usual diet.

Outcomes are sweet taste preferences, sweet food intakes, sweet taste intensity ratings, ratings of hunger and thirst and ratings of compliance with the intervention.

Sweet taste perceptions

Pleasantness, desire to eat and sweet taste intensity will be assessed on each test day using a taste perception test. Participants are instructed to consume bite-sized portions of six different foods, comprised of both sweet and non-sweet items of a range of textures. Participants are asked to rate pleasantness ('How PLEASANT does this food taste to you right now?', response anchors: 'not at all pleasant', 'extremely pleasant'), desire to eat ('Now, rate how strong your DESIRE TO EAT more of this food is right now?' response anchors: 'not at all strong', 'extremely strong') and sweet taste intensity ('How SWEET does this food taste to you right now?' response anchors: 'not at all sweet', 'extremely sweet') using 100 mm visual analogue scales (VAS). Data are provided in mm from 0 to 100mm.

Sweet food intake

Sweet food intake will be assessed on each test day using an ad-libitum cold buffet-style breakfast. Participants will be presented with a variety of sweet and non-sweet foods and invited to consume as much or as little as they wish. All foods provided are commonly consumed for breakfast in the UK and have been previously been used to illustrate changes in intake over time. For each participant, foods are individually weighed before and after breakfast to allow calculations of the percentage weight consumed from sweet foods and sweet foods and beverages, percentage of energy consumed from sweet foods and sweet foods and beverages, the weight of sugar consumed from foods and from foods and beverages, and percentage of energy consumed from sugar from foods and foods and beverages. Data are provided in grams, kJ, and as percentages as appropriate.

Appetite

Hunger and thirst will be assessed using self-report ratings of 'How HUNGRY are you right now?', response anchors: 'not at all', 'extremely'; 'How FULL are you right now?', response anchors: 'not at all', 'extremely'; and 'How THIRSTY are you right now?', response anchors: 'not at all', 'extremely'; using 100 mm visual analogue scales (VAS). Data are provided in mm from 0 to 100mm.

Compliance

Compliance with the intervention instructions will also be assessed at the end of the intervention period. Participants will be asked how well they adhered to the allocated diet ('How well did you adhere (manage to keep) to your allocated diet?', response anchors: 'not at all', 'extremely'), how difficult they found it to adhere to the allocated diet ('How difficult did you find it to adhere (manage to keep) to your allocated diet?', response anchors: 'not at all', 'extremely') and how different their allocated diet was from their usual diet ('How different was your allocated diet from your usual diet?', response anchors: 'not at all', 'extremely').

Responses will again be made using 100 mm VAS scales. Data will again be provided as mm from 0 to 100mm.

Analyses

Data for all outcome measures will be processed and collated using Microsoft Excel by one researcher who will remain blind to participant condition until all data have been checked and are confirmed.

Following unblinding, data will first be described, by participant group.

Prior to all analyses, data will be checked for normality and other violations of parametric assumptions. Violations will be addressed using corrections, e.g. Greenhouse Geisser, transformations or non-parametric tests will be used where appropriate.

For the taste perception measures, ratings for pleasantness, desire to eat and sweet taste intensity will be averaged across all sweet and non-sweet foods tested, resulting in two scores per outcome measure, one for sweet and one for non-sweet foods. These will then be analysed using 3 condition (increase sweet food consumption, decrease sweet food consumption, no diet change) x 2 time (day 0, day 7) x 2 food type (sweet foods, non-sweet foods) repeated-measures ANOVAs.

For sweet food intake measures, the weight of foods consumed in grams, will be calculated by subtracting the weight of foods returned to the kitchen from the amount served at breakfast, and used to calculate the percentage weight consumed from sweet foods and the percentage weight consumed from sweet foods and beverages. Manufacturer's information will then be used to calculate the percentage of energy consumed from sweet foods, percentage energy consumed from sweet foods and beverages, the weight of sugar consumed from foods, the weight of sugar consumed from sweet foods and beverages, the percentage of energy consumed from sugar from foods, and the percentage energy consumed from sugar from foods and beverages. Intake will then be analysed using 3 condition (increase sweet food consumption, decrease sweet food consumption, no diet change) x 2 time (day 0, day 7) repeated-measures ANOVAs.

Appetite will be assessed using 3 condition (increase sweet food consumption, decrease sweet food consumption, no diet change) x 2 time (day 0, day 7) repeated-measures ANOVAs, for each of the three measures.

Compliance will be assessed using 3 condition (increase sweet food consumption, decrease sweet food consumption, no diet change) x 2 time (day 0, day 7) repeated-measures ANOVAs.

Correlations between measures in the taste perception test and the subsequent intake measure will also be conducted.

Analyses will be undertaken on an intention-to-treat basis, with missing data imputed using models based on gender, age and baseline data. Per-protocol analyses may also be undertaken dependent on participant drop out and self-reported compliance.

Analyses will be conducted in SPSS (version 28.0.0.0) or Stata (version 15), as required. Data will be presented as means and standard deviations. Significance will be set at $p = 0.05$.

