that are experienced as tasting sweet v. not sweet by each individual. For those in the control arm, no dietary change was required. Participants were simply asked to 'Continue consuming all foods and drinks that you were consuming last week'. Intervention instruction guides were provided to participants in written form for them to take away and refer to as they wished. In addition, on receipt of their instructions, participants were reminded that the aim of the study (as disclosed during consent procedures) was to investigate the effects of a dietary change and were asked to make this change as substantial as possible to enhance our chances of finding effects. The researcher in contact with participants was not aware of the specific instructions given, but contact details of an additional researcher were also given should questions arise during the course of the study. Participants were asked to undertake the intervention for 6 d (days 1–6) with outcomes assessed on day 0 and day 7.

Outcomes

Our primary outcomes were pleasantness and desire to eat for sweet and non-sweet foods and sweet food intake assessed at an ad libitum cold, buffet-style, breakfast meal.

Secondary outcomes were perceived sweet taste intensity of the sweet and non-sweet foods, self-reported adherence to the allocated diet and measures of appetite.

Pleasantness and desire to eat

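### The SAP gives no rule for switching to transformations or rank tests, and its text places that choice after unblinding and by-group description

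*SAP*

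**What the plan says.** All of this is in the SAP under Analyses, in this order.

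- Blinding covers the handling of the data set. It applies to a single researcher, "who will remain blind to participant condition until all data have been checked and are confirmed".
- The step that comes next is descriptive, with arms known: "Following unblinding, data will first be described, by participant group".
- A new paragraph then brings in the assumption check, which is not said to be blinded: "Prior to all analyses, data will be checked for normality and other violations of parametric assumptions".
- Remedies come last. The only one named is an adjustment to the ANOVA itself, Greenhouse-Geisser; the others are left general, in that "transformations or non-parametric tests will be used where appropriate".

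The planned models follow. Taste ratings are analysed by condition "x 2 time (day 0, day 7) x 2 food type (sweet foods, non-sweet foods) repeated-measures ANOVAs". For the buffet breakfast, "Intake will then be analysed using 3 condition" by two time points, again in repeated-measures ANOVAs. The effect of interest is therefore condition × time, with food type added for the ratings.

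The Protocol (Outcomes) makes these outcomes primary: "Our primary outcomes were pleasantness and desire to eat for sweet and non-sweet foods and sweet food intake". The SAP lists eight intake measures (two sugar weights and six percentages), so with the two ratings the open choice arises for 2 + 8 = 10 primary measures.

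**The concern.** The SAP has a blinded stage for checking data, but the one choice of method that depends on the data is not placed inside it. Read in order, the analyst sees summaries by arm and then decides, outcome by outcome, whether to keep the ANOVA, transform or use ranks. No test, threshold, transformation or rank procedure limits that decision.

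Two things are at stake. The first is the false-positive rate, if the choice is influenced by which method favours an effect. The second is the question being answered. Some familiar rank tests on raw scores (Kruskal-Wallis on day 7 alone, or Wilcoxon or Friedman across time) do not compare change between the randomised arms, and the SAP does not exclude them. Sugar weights cannot be negative and percentages are bounded, so a failed normality check on the intake measures is plausible, although neither document gives their distribution.

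**Working it through.** **1. Timing.** The word *first* makes by-group description the opening step after unblinding. The assumption check comes in the next paragraph and is tied to preceding the analyses, not to preceding unblinding. Nothing says that it is blinded. That it follows unblinding is a strong inference from the order of the text, not a stated fact.

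**2. The one named correction does nothing here.** The Greenhouse-Geisser epsilon has lower bound 1/(k − 1) for a within-subject factor with k levels. Time and food type both have k = 2, so the bound is 1/(2 − 1) = 1 and no correction is made. The remedies that can act are the unspecified ones.

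**3. Can a rank test address the interactions?** Yes, if it is applied to the right score.
- With two time points, let d = day 7 − day 0 for each participant. The condition × time F equals the one-way ANOVA F on d, with 2 and N − 3 degrees of freedom (2 and 97 for N = 100). On a generated data set both came to 0.04178. Kruskal-Wallis on d is therefore a rank test of differential change.
- For the three-way term, use c = d(sweet) − d(non-sweet) in the same way.

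The SAP names neither.

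**4. Type I error.** The plan's own figure is a significance level of 0.05.
- From the documents: 40 per intervention group (Protocol, Participants) and a 2:2:1 final ratio (Protocol, Procedure), taken as 40:40:20.
- Assumed, because the documents do not give them: the distributions and the within-person correlation r.

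| Data, no true effect | Runs | One fixed method | Shapiro-Wilk rule | Smallest p among interaction tests | Same, plus Kruskal-Wallis on day 7 |
|---|---|---|---|---|---|
| Normal ratings, SD 15 mm, r 0.6 | 4,000 | 4.6–5.2% | 5.3% | 7.3% (of four) | 11.4% |
| Log-normal, log SD 0.6, r 0.6 | 4,000 | 4.6–5.2% | 4.9% | 8.3% (of four) | 12.3% |
| Log-normal, log SD 0.7, r 0.6 | 6,000 | 4.7–5.2% | 5.4% | 8.4% (of three) | not run |
| Beta(1.2, 0.8) percentages, r 0.6 | 2,000 | – | – | 8.0% (of three) | not run |
| Log-normal, r 0.4 to 0.8 | – | about 5–6% | about 5–6% | 8.6–9.5% (of three) | not run |

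A dash marks a figure not recorded. The three tests are ANOVA, ANOVA on logs and Kruskal-Wallis; the four add ANOVA on square roots.

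The Monte Carlo standard error at 5% is √(0.05 × 0.95 / 4,000) = 0.34 points, or 0.28 points with 6,000 runs. The 5.4% is thus (5.4 − 5.0)/0.28 = 1.4 standard errors above nominal and cannot be told apart from it. The 7.3% to 9.5% figures can.

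**5. Day-7-only ranks.** One arm was given a higher level on both days by 0.5 on the latent person effect, which is 0.5 × √0.6 × 15 = 5.8 mm, with no difference in change (3,000 runs). Kruskal-Wallis on day 7 rejected in 35% of runs; on change it rejected in 4.3%. The 35% depends on that assumed imbalance. Without it, the day-7 test held 5.2%.

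**The case against.** The strongest reply is that the SAP ties the switch to violations of assumptions, not to results. The simulation closest to that is the fixed normality rule, which shows no detectable inflation. The larger figures need an analyst to run several tests and keep the most favourable, which the SAP does not propose. This stands, and it limits the size of the concern: harm comes from unrestricted choice, not from switching as such.

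Three stronger readings are tempting, and the documents do not support them.

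- *Standard rank tests cannot test the planned interactions.* In this design they can, as step 3 shows. The fault is that the SAP does not say which score would be ranked. Nor does it say that it would use single-day or within-arm tests.
- *The check is stated to follow unblinding.* It is only written after it, and descriptive summaries by arm are not test results.
- *The method was chosen in knowledge of the results, because the SAP is dated 26 April 2024 and data collection ended in March 2024.* No unblinding date is given, so this cannot be concluded.

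It is also fair to say that replacing the repeated-measures ANOVA by a baseline-adjusted model is partly a modelling preference. Condition × time already compares change between arms, and fixing that ANOVA as the sole primary method would also remove the open choice.

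**Conclusion.** The concern holds in limited form. For each primary outcome the SAP leaves the analysis method open, gives no rule for closing it, and sets the decision at a point where allocation is likely to be known. Followed by a fixed rule, the plan costs little: about 5% to 6% type I error. With unrestricted choice, the worst case is about 8% to 10% per outcome for skewed data (7.3% for normal ratings), and 11.4% to 12.3% if a day-7-only rank test is also admitted. These figures rest on assumed distributions and on correlations of 0.4 to 0.8 (0.6 for the day-7 figures), and they are not estimates of what this trial's analysis did. The change is worth making because it removes a possible source of bias cheaply, not because the plan as written is shown to inflate error.

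**What to change.** 1. Move the assumption check into the existing blinded data-check stage, with a stated rule, and record the decision before unblinding. Use pooled or dummy-coded data. Pooled is safer, because with a 2:2:1 ratio the smallest coded arm can be recognised as the control.
2. Fix one primary between-arm model per outcome: day 7 adjusted for day 0. For the taste ratings, apply it to the sweet score, the non-sweet score and their difference, so that the food-type question is kept.
3. If residuals are clearly non-normal or variances unequal, keep the model and use robust (for example HC3) or bootstrap confidence intervals.
4. Report transformed analyses, or rank analyses on change scores (for the ratings, also on the sweet-minus-non-sweet difference in change), only as labelled sensitivity analyses.

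If the data are already unblinded, report when each method was chosen and give the fixed-model result alongside.

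The cost is some SAP wording and a few lines of SPSS or Stata code. The small downside is that skewed outcomes keep a mean-based estimate.

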The study was run from both the University of Bristol, UK (February 2018–May 2018), and from Bournemouth University (January 2023–May 2023, October 2023–March 2024). The initial study began at the University of Bristol and, following disruptions due to COVID-19, was continued later at Bournemouth University. Data collection was carried out at the Nutrition and Behaviour Unit at the University of Bristol and the Eating Behaviours Laboratory at Bournemouth University. Participants visited the testing site fasted and rested on day 0 and day 7 during pre-booked time slots. Visits were scheduled between 08.00 and 11.00, and the timeslots remained the same on both occasions. Upon arrival, participants were seated individually at a table where they were presented with the taste perception test. After completing this test, participants received their cold buffet-style breakfast. The entire procedure lasted approximately 30 min and was repeated exactly on both testing occasions, with three exceptions. At the end of day 0 following all data collection, participants were provided with their dietary intervention. On day 7, participants also completed the adherence questions before the taste perception test, and they were asked about any difficulties experienced over the intervention period. After their breakfast, they were also debriefed about the purpose of the research and thanked for participating in the study. To maintain a researcher-blinded study design, an independent researcher with no contact with participants randomised participants to one of the trial arms using a random number generator. Participants were randomised at a ratio of 1 (increase): 1 (decrease) at the University of Bristol and subsequently at a ratio of 1 (increase): 1 (decrease): 1 (no change) at Bournemouth University, to result in a final sample with a ratio of 2 (increase): 2 (decrease): 1 (no change). Group allocation was concealed using white sealed, opaque envelopes, and throughout the trial, the researcher in direct contact with participants remained unaware of each participant's group allocation. To support the blinding,

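### The primary ANOVAs use day 0 only as a level of time and omit site: precision is lost for increase v decrease, and contrasts with control are exposed to site differences in change

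*SAP*

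**What the plan says.** The Protocol (Outcomes) states: "Our primary outcomes were pleasantness and desire to eat for sweet and non-sweet foods and sweet food intake". The SAP (Analyses) averages the ratings into one sweet and one non-sweet score and continues: "These will then be analysed using 3 condition (increase sweet food consumption, decrease sweet food consumption, no diet change) x 2 time", with the third factor given as "2 food type (sweet foods, non-sweet foods) repeated-measures ANOVAs". For intake: "Intake will then be analysed using 3 condition (increase sweet food consumption, decrease sweet food consumption, no diet change) x 2 time". Neither model has a baseline covariate or a term for site or period. The only other stated use of day 0 is for missing values: "missing data imputed using models based on gender, age and baseline data".

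The Protocol (Procedure) gives the facts that matter for the model:

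- **Timing of day 0.** "At the end of day 0 following all data collection, participants were provided with their dietary intervention".
- **Allocation.** "Participants were randomised at a ratio of 1 (increase): 1 (decrease) at the University of Bristol and subsequently" at 1:1:1 at Bournemouth, "to result in a final sample with a ratio of 2 (increase): 2 (decrease): 1 (no change").
- **Sites.** Bristol ran in 2018 and Bournemouth in 2023–2024. At Bristol a researcher talked the dietary change through with participants as well as giving the written guide; at Bournemouth they received only the guide.

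**The concern.** There are two separate issues.

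**Precision.** With two time points, condition x time is a comparison of mean change between arms. Day 0 was measured before the diet instructions were handed over, so it is a proper covariate. Regressing day 7 on it is at least as precise in large samples, and the data are already in hand.

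**Site.** By the stated ratios, half of each intervention arm and none of the control arm comes from Bristol. If participants at the two sites change by different amounts over the week for reasons unrelated to diet, the planned model reads part of that as a difference from control. The gap in years and the different delivery of instructions make such a difference plausible. The documents do not show that one exists.

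**Working it through.** **Inputs from the documents.** Two-sided alpha 0.05, power 0.8, change 6–9 mm, SD about 13–17 mm, forty per intervention group (Protocol, Participants); allocation by site (Protocol, Procedure). Forty per intervention group and 2:2:1 imply 40/40/20, with Bristol 20/20/0 and Bournemouth 20/20/20. The 50% Bristol share follows from the ratios at any total.

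**Assumed.** r, the day 0–day 7 correlation, with equal variances at both times; the size of any site difference.

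**1. The plan's own figure.** Two-sample n per arm = 2(1.96 + 0.84)²/(δ/SD)². It gives 33 at 9/13 mm, 63 at 7.5/15 mm and 127 at 6/17 mm. Forty needs δ/SD = 0.626, for example 9 mm with SD 14.4 mm. A paired t calculation at 6/13 mm gives 39. So 40 can be reached from the stated ranges, but not uniquely, and the Protocol does not name the comparison that was powered.

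**2. Day 0.** The variance of a change score is proportional to 2(1 − r); that of day 7 adjusted for day 0 is proportional to 1 − r². The ratio, adjusted to change score, is (1 − r²)/[2(1 − r)] = (1 + r)/2. Power for increase v decrease (40 v 40, normal approximation) is shown from two starting points:

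| r | Variance ratio | From an assumed 80% | From 61% (7.5 mm, change SD 15 mm) |
|---|---|---|---|
| 0.3 | 0.65 | 94% | 79% |
| 0.5 | 0.75 | 90% | 73% |
| 0.7 | 0.85 | 86% | 68% |
| 0.9 | 0.95 | 82% | 63% |

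For the three-way rating term the relevant correlation is that of the sweet-minus-non-sweet difference, rD = (r − c)/(1 − ρ). Here ρ is the sweet/non-sweet correlation on one day and c the same across days. Assuming r 0.5–0.7, ρ 0.3–0.5 and c 0.2–0.45 with c no larger than ρ, rD runs from (0.5 − 0.45)/0.5 = 0.10 to (0.7 − 0.2)/0.5 = 1.00. The variance ratio is then 0.55–1.00, so the gain could be large or nil.

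**3. Site.** Let mean change differ between sites by D mm. The intervention arms carry D/2 and control carries 0. Each contrast with control shifts by D/2, and increase v decrease shifts by 0.

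- At D = 4 mm the shift is 2 mm. Simulation without a diet effect (level SD 15 mm) gave 2.05–2.08 mm. The 2-df condition x time test rejected in 7.2% (r = 0.5) and 8.6% (r = 0.7) of runs instead of 5%. If 13–17 mm is read as the SD of change, the noncentral F distribution (noncentrality 64/SD²) gives 6.6–7.9%.
- With day 0 and site in the model, the shift was 0.01–0.08 mm and rejection 5.2% and 4.8%.
- A constant site difference in level cancels in condition x time. It does not cancel in a day 0 covariate model without site: an assumed 6 mm shifts contrasts with control by about (1 − r) × 6/2, that is 1.5 mm at r = 0.5 and 0.9 mm at r = 0.7.
- In condition x time x food type, a site change common to sweet and non-sweet foods also cancels. Only a site change that differs by food type remains. Intake and the rating condition x time term have no such protection.

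**4. Price of the site term.** For a contrast with control, the variance in units of the residual variance is 1/40 + 1/20 = 0.075 without site. With site it is 1/40 + 1/20 + (1/4)(1/40 + 1/40) = 0.0875, a factor of 7/6. Increase v decrease stays at 0.05. With both terms, the net ratio to the planned analysis is (7/6)(1 + r)/2 = 0.76, 0.88, 0.99 and 1.11 at r = 0.3, 0.5, 0.7 and 0.9, with break-even at r = 5/7.

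**The case against.** **A valid test needs no replacing.** Condition x time is unbiased for increase v decrease and fits a sample size planned on changes. The gain from day 0 is unknown and, at r = 0.9, takes 80% only to 82%. This stands as a limit on size. It does not make the adjustment a matter of taste: the precision of increase v decrease improves at any r below 1, for one degree of freedom and no new data.

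**The ratings are partly protected.** This stands. The 2 mm shift and the 7–9% rejection belong to condition x time and do not carry over to the three-way term.

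**The site term misses the best-documented difference.** The Protocol says interventions and measures were otherwise identical at the two sites, so delivery of instructions is the obvious candidate, and it would alter intervention strength. This stands in part. If both diets acted 4 mm more strongly at Bristol, in opposite directions, each contrast with control would still differ from its Bournemouth value by 2 mm with an additive site term. Only an analysis of Bournemouth alone shows this.

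**Stronger readings.** A reader might infer that the planned ANOVAs are invalid, that the whole trial is confounded with site, or that power against control falls short of a planned value. The documents support none of these. Increase v decrease was randomised 1:1 at both sites, and no power against control is planned anywhere.

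**Conclusion.** The point holds as a recommended improvement, not as an invalidating error. For increase v decrease the planned analysis is sound but has 2/(1 + r) times the variance it needs: 1.33, 1.18 and 1.05 at r = 0.5, 0.7 and 0.9. Contrasts with control, and the 2-df condition x time test that includes control, carry half of any site difference in change. For the three-way rating term this applies only to a site change that differs by food type.

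The allocation facts come from the Protocol. The value of r, the site differences and the 80% starting point are assumptions; at 7.5/15 mm the starting point is 61%. Whether a site difference in change exists can be examined only in the data.

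**What to change.** For each primary measure, fit day 7 = condition + day 0 value + site. For each rating, fit two such models: the mean of the sweet and non-sweet scores, and sweet minus non-sweet, each with its own day 0 value and site. Enter the covariate and the site term together, because the covariate alone lets part of a level difference between sites into the contrasts with control.

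As a sensitivity check, repeat the contrasts with control in Bournemouth alone, where all three arms were randomised 1:1:1.

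Report this as a disclosed adjusted analysis beside the planned ANOVAs and do not substitute it for them: the SAP is dated 26.04.24 and data collection ended in March 2024.

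**Cost.** Day 0 takes one degree of freedom and assumes a roughly linear relation. Both terms run in the software the SAP names. Site costs increase v decrease essentially nothing but multiplies the variance of contrasts with control by 7/6, a net loss there if r exceeds about 0.71. The Bournemouth-only check compares 20 with 20, so its variance before day 0 adjustment is 0.10/0.075 = 4/3 of the planned contrast. It should be read for consistency, not as a test in its own right.

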participants were asked not to disclose any information about the instructions they received to the researcher conducting the testing. Although it was impossible to blind the participants to their group allocation, they were unaware of the true aim of the trial and the instructions received by other participants. Prior to commencement, the study was registered on Clinicaltrials.gov (Initial Study ID: NCT03427658, registration on 9 February 2018, Complete Study ID: NCT05672017, registration on 5 January 2023). We adhered to our trial registrations in all aspects with the exception that sweet food intake was measured only at breakfast rather than at breakfast and lunch as proposed in the registration for the initial study. The study was run using identical interventions and measures in both locations, with the exception that in Bristol, participants discussed their dietary change with a (independent) researcher and were given the written instruction guide, while in Bournemouth, participants were only provided with the written instruction guide, which included a contact to ask questions

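### No model includes site, although only Bournemouth randomised to control, so control comparisons and the three-condition tests partly compare sites

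*SAP*

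**What the plan says.** The Protocol (Procedure) describes two stages. At Bristol, February–May 2018: "Participants were randomised at a ratio of 1 (increase): 1 (decrease) at the University of Bristol". At Bournemouth, January–May 2023 and October 2023–March 2024, allocation was 1:1:1 with a no-change arm. The two stages are meant "to result in a final sample with a ratio of 2 (increase): 2 (decrease): 1 (no change"). The same section says "The study was run using identical interventions and measures in both locations", with one exception: Bristol participants discussed the dietary change with an independent researcher and received the written guide, while Bournemouth participants received only the guide, with a contact for questions.

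The SAP (Analyses) does not mention site.
- Ratings: "These will then be analysed using 3 condition (increase sweet food consumption, decrease sweet food consumption, no diet change) x 2 time", crossed with food type.
- Intake: "Intake will then be analysed using 3 condition (increase sweet food consumption, decrease sweet food consumption, no diet change) x 2 time".
- Appetite: "Appetite will be assessed using 3 condition (increase sweet food consumption, decrease sweet food consumption, no diet change) x 2 time".
- Missing data: "missing data imputed using models based on gender, age and baseline data".

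The SAP does not say in so many words that the two sites are pooled. That is inferred from the single final sample in the Protocol and from the three-condition models.

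**The concern.** The chance of being allocated to control was 0 at Bristol and 1/3 at Bournemouth. Randomisation therefore protects a comparison with control only within Bournemouth. The planned models treat all participants as one three-arm randomised sample, so Bristol participants, who could not have been allocated to control, are compared with it as if they could have been. Site, calendar period and mode of delivery cannot be separated from one another, and all three differ between half of each active arm and the whole control arm.

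This reaches the primary outcomes (pleasantness, desire to eat, sweet food intake), because the three-condition ANOVAs are the only between-condition tests the SAP names for them. A shift common to both active arms at Bristol could appear as an effect of changing sweet intake in either direction, or could hide one.

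**Working it through.** **Inputs.** From the Protocol: 40 per intervention group, two-sided 0.05, power 0.80, change 6–9 mm, SD 13–17 mm (Participants); allocation ratios by site (Procedure). Assumed: the site difference in change, which the documents do not give.

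**The plan's own figure.** n per group = 2(1.96 + 0.84)² SD²/δ². With 9 mm and SD 14 mm this is 38; with 8 mm and SD 13 mm it is 42. The stated 40 is thus reached for some pairs inside the stated ranges (full span 33 to 127). It serves here only to set cell sizes.

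**Cells.** Let b and m be the numbers per arm at Bristol and Bournemouth. Then (b + m):(b + m):m = 2:2:1 gives b = m. Half of each active arm and none of control come from Bristol, whatever the sample size. With 40 per active arm the cells are 20/20 at Bristol and 20/20/20 at Bournemouth.

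**Bias.** Let D be the Bristol-minus-Bournemouth difference in mean change, the same in both active arms and with no diet effect. Then:
- active minus control: (20/40)·D − 0 = D/2;
- increase minus decrease: D/2 − D/2 = 0.

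A site difference that is constant over time cancels in condition × time. It does not cancel in the condition main effect or in compliance, which has no baseline: "Compliance with the intervention instructions will also be assessed at the end of the intervention period". In condition × time × food type, a shift common to sweet and non-sweet foods cancels, and half of any food-specific difference remains.

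**Omnibus type I error, condition × time.** Simulated normal change scores, no condition effect, 60,000 trials per setting:

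| Site shift (SD of change) | mm at SD 15 | Bias in each control contrast (SD) | Type I error, no site term |
|---|---|---|---|
| 0 | 0 | 0 | 5.0% |
| 0.1 | 1.5 | 0.05 | 5.2% |
| 0.2 | 3 | 0.1 | 6.0% |
| 0.4 | 6 | 0.2 | 9.4% |
| 0.6 | 9 | 0.3 | 14.3% |

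With site in the model the rate is about 5% in every row. Over SD 17 down to 13 mm, a 3 mm shift gives 5.7–6.6%, 6 mm gives 8.0–10.6% and 9 mm gives 12.7–17.8%.

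**Condition × time × food type** (40,000 trials per setting, SD 15 mm). A shift common to both food types gives 4.9–5.1%. A sweet-only shift of 3, 6 or 9 mm gives 6.0%, 9.4% and 14.7% if sweet and non-sweet changes correlate 0.5, and 5.4%, 6.9% and 9.8% if they are uncorrelated.

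**Precision** (variances in units of SD²).
- Active versus control, no site term: 1/40 + 1/20 = 0.075.
- With site: the mean of the active arms against control is informed only by Bournemouth, 1/40 + 1/20 = 0.075. Half of the increase–decrease difference adds 0.25 × 0.05 = 0.0125. The total is 0.0875, and √(0.0875/0.075) = 1.08.
- Bournemouth only: 1/20 + 1/20 = 0.10.
- Increase versus decrease: 1/40 + 1/40 = 0.05, with or without site.
- Condition × site in the active arms: 4 × 1/20 = 0.20.

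**Delivery effects that differ by arm.** If Bristol delivery adds +6 mm in increase and −6 mm in decrease, the site coefficient is 0 and the control contrasts shift by +3/−3 mm with or without the site term. If it adds +6 mm in increase only, the shifts are +3/0 mm without site and +1.5/−1.5 mm with it.

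**The case against.** The best opposing case accepts the facts and disputes the weight. Inflation becomes material only at about 0.4 SD, which is 6 mm at SD 15 mm, the lower end of the change the trial was powered on; nothing in the documents suggests that two UK sites differ that much in change over a week. Participants act as their own baseline, food order and time slots were fixed within person, and measures were identical, so stable differences drop out of condition × time. The one documented difference, delivery, would more naturally strengthen each arm's own instruction than move both arms the same way. If diet has no effect, better adherence to it produces no false positive; if it has one, the pooled estimate averages over two modes of delivery. An additive site term does not cure that and can spread a one-arm effect into the other contrast.

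Much of this stands. The error rates describe a site or period shift common to both active arms, and should not be read as estimates of a delivery effect. The size of any shift is unknown and may be small. The site term alone is not sufficient, so the within-Bournemouth comparison is needed as well. What does not follow is that site can be left out: it determined the allocation ratio, one arm is absent from one site and period, and nothing in the documents justifies assuming equal change at both.

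**Conclusion.** The concern holds. Half of each active arm and none of control come from a site and period where control could not be allocated, and no planned model or imputation accounts for this. The 50% versus 0% split follows from the stated ratios alone. The bias in a control contrast in change is half the site difference in change. The omnibus error rates of 5.2% to 14.3% rest on cells of 20/20 and 20/20/20, normal change scores, and assumed common site shifts of 0.1 to 0.6 SD; they are small for small shifts and material from about 0.4 SD. Increase versus decrease is not biased. The SAP names no pairwise contrasts, so the problem applies first to the three-condition tests and then to any follow-up against control. It needs correcting because of the design, not because a large site shift has been shown.

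**What to change.** 1. Add site and site × time to the models for ratings, intake and appetite, and for ratings also site × food type and site × time × food type. For compliance, measured once, add site as a between-subject term only. The Bristol control cell is empty, so condition × site cannot be fitted across all three arms.
2. Include site in the imputation model.
3. Report the concurrently randomised, Bournemouth-only three-arm comparison beside every pooled comparison that involves control.
4. In the two active arms, estimate condition × site × time with a 95% confidence interval, since an additive site term does not remove a delivery effect that differs by arm. Do not use it as a test to decide on pooling, because power is low.
5. State that these analyses were specified after data collection, which ended in March 2024; the SAP is dated 26.04.24.

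**Cost.** Site is known for every participant, so no data are added. At SD 15 mm, the difference detectable with 80% power (noncentral t) for a control contrast goes from 11.6 mm pooled to 12.6 mm with site and 13.5 mm for Bournemouth only; for condition × site in the active arms it is 19.0 mm. The variance of increase versus decrease does not change. The post hoc label is unavoidable.
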